7.3. Treatment for AML and ALL

Among the therapeutic approaches, patients can be selected for an intensive treatment, which consists of either systemic or local (including intrathecal) chemotherapy.³³ Besides chemotherapy, other types of treatment can be recommended according to patient status, including hematopoietic stem cell transplantation (HSCT); investigational products offered in clinical trials and targeted therapy. According to the patient's characteristics, patients should first undergo an induction therapy to achieve complete remission, with a subsequent consolidation therapy in order to achieve a negative minimal residual disease (MRD).

Although advances in the treatment of AML have led to significant improvements in outcomes for younger patients, prognosis in the elderly who account for the majority of new cases remains poor. Even with current treatments, as much as 70% of patients 65 years or older will die of their disease within 1 year of diagnosis.⁴ Except for those with acute promyelocytic leukemia, approximately 50% of patients under 60 years and 90% of patients over 60 years will.³

The main induction therapy for AML changed minimally over the past 40 years and consist of the 7+3 regimen, which combines 7 days of continuous infusion cytarabine with 3 days of anthracycline.^{34,35} The combination of fludarabine, cytarabine, Granulocyte colony stimulating factor (G-CSF) and idarubicin (FLAG-IDA), which was traditionally used for the treatment of relapse, has also been shown to be a reasonable alternative to standard induction regimens and results in similar CR rates and overall survival (OS) with higher rates of CR after a single course.⁴ Nevertheless, the treatment approach for elderly patients with AML are not a consensus. These patients usually have a poor response to the conventional regimens, and in some cases are indicated for supportive care and palliative chemotherapy.

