- Relapse-free survival (RFS) for newly diagnosed AML patients – considered as measured from the date of achievement of a remission until the date of relapse or death from any cause; patients not known to have relapsed or died at last follow-up are censored on the date they were last examined. Defined only for patients achieving CR, or CRI.

- Event-free survival (EFS) of newly diagnosed AML and relapsed/refractory B-cell ALL patients – considered as the measured from the date of initiation of treatment to the date of primary refractory disease, or relapse from CR, or CRi, or death from any cause; patients not known to have any of these events are censored on the date they were last examined

All computations and generation of tables, listings, graphics, and data for figures will be performed using R® version 3.5.3 or newer version (R Core Team), or a comparable statistical software package.

Medical Dictionary for Regulatory Activities Terminology (MedDRA) version 2.1 (V2.1) or newer version will be used as a standardised medical terminology. Medicinal product names will be codified using World Health Organisation Drug Dictionary (WHODrug), a dictionary maintained and updated by Uppsala Monitoring Centre (UMC).

The resource utilization (eg, number of hospital admissions, hospitalization period, procedures during hospital admissions) will be presented as mean number per patient per year (PPPY). According to the sample distribution, the data will be presented with a standard deviation (SD) or a 95% confidence interval (95% CI), which will be estimated either by Poisson regression or Gama distribution. The PPPY will be calculated as the sum of all event observed in the cohort divided by the total follow-up period (in years) of all patient in the cohort (including those who did not present the event).

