8.2. Setting

8.2.1. Study Time Period

For this study, data from patients treated at public or private healthcare facilities in Argentina, Brazil, Chile, Colombia, diagnosed with R/R B-cell ALL or AML between 01 January 2015 and 31 December 2019 will be considered for the analysis.

The eligibility period of 5 years was determined to increase the overall patient representativeness, and to allow ample follow-up to assess survival outcomes.

The study will be conducted in approximately 15 sites distributed across Argentina, Brazil, Chile, and Colombia, and is expected to enroll approximately 700 patients with R/R B-cell ALL and AML in a consecutive matter. To assure the representativeness of each country, the number of sites and the total expected enrolled patients will be limited according to the country, considering the prevalence/incidence of the diseases.

Data collection will occur in a period of up to 12 months following the independent ethics committee (IEC)/ institutional review board (IRB) approval and study set up. Patients will be consecutively enrolled, considering both target population, with no set proportion of AML and R/R B-cell ALL patients to be included in the study. However, it is expected a higher proportion of AML patients in the cohort. The study period will comprise since diagnosis date (index date) until the study enrollment or death, whichever comes earlier.

[figure not shown]

Figure 1. Study time period.

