8.7. Data Analysis

Analyses will be descriptive in nature, as no hypothesis is being tested. Disease staging, comorbidities, demographic, clinical characteristics will be described at the date of diagnosis and/or treatment initiation for patients diagnosed with B-cell ALL R/R or AML. Treatment and clinical information will be assessed up to the most recent data available at the study enrollment. The treatments will be described in sequence according to the chronological order of administration. The duration through the number of cycles will be evaluated. Dose reduction information will also be collected. All analysis, including subgroup assessment, will be performed according to the data availability.

Continuous variables will be described as mean and standard deviation (SD), and/or as median, minimum, maximum, interquartile range (IQR, 25th and 75th percentiles). Categorical variables will be described by simple and cross contingency tabulation, with absolute frequencies and percentages. Missing values will be included in the denominators for the calculation of percentages and missing categories will be presented.

Follow-up period will be considered the time (in years) elapsed since B-cell ALL R/R or AML diagnosis until the study enrollment. It will be summarized as a continuous variable.

All time-to-event analysis will be described using Kaplan Meier methods and plots, if appropriate. The following definition and parameter analysis will be considered:

- Time to next treatment (TTNT) – considered as the time from the start date of the front-line therapy to the start date of a subsequent line of therapy. Patients without a subsequent line of therapy will be censored at study enrollment, last visit, last contact, or death, whichever comes first. It will be presented in months.
- Overall survival (OS) – considered as death from any cause from the time of initiation of diagnosis or treatment [12,13]. Patients not known to have died will be censored at study enrollment, last visit, last contact, whichever comes later. The median OS and, if feasible, the % of alive patients in 1, 3- and 5-years follow up of newly diagnosed AML and R/R B-cell ALL patients will be assessed.

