The resource utilization (e.g., number of hospital admissions, hospitalization period, procedures during hospital admissions) will be presented, if possible, as mean number per patient per year (PPPY). According to the sample distribution, the data will be presented with a standard deviation (SD) or a 95% confidence interval (95% CI), which will be estimated with the most appropriate distribution, which may include Negative Binomial, Poisson or Gama distribution. The statistical distribution will be chosen with quantil-quantil plots (QQplots).

For each resource utilization, the PPPY will be calculated as the sum of all utilizations, divided by the follow up, for each patient. It will be summarized as a continuous variable.

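### Resource use per patient-year (PPPY): the SAP replaces the protocol's pooled rate with a mean of per-patient ratios, and the follow-up it divides by has conflicting end points

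*SAP*

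**What the plan says.** **The estimator.** Protocol Section 9.7 makes PPPY the "sum of all event observed in the cohort divided by the total follow-up period (in years) of all patient in the cohort", and adds that patients without the event count in the denominator. SAP Section 8.7 says that "the PPPY will be calculated as the sum of all utilizations, divided by the follow up, for each patient", followed by "It will be summarized as a continuous variable". The SAP names the mean as the PPPY statistic, to be shown where possible. Its 95% interval comes from whichever of the negative binomial, Poisson, Gamma or another distribution looks best on QQ plots.

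**The denominator.** The documents end follow-up in several ways:

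- Protocol 9.7 and SAP 8.7, where PPPY is defined: diagnosis to study enrollment, with no mention of death.
- Protocol 9.1 and 9.2, SAP 8.1 and 8.2.1: enrollment or death. SAP 8.2.1 reads "The study period will comprise since diagnosis date (index date) until the study enrollment or death, whichever comes earlier".
- SAP 8.2.3: end of the study period or last available information.
- SAP 8.7.2, item 13 (resource use): loss of follow-up or death.
- Protocol Section 4 (abstract): the earliest of enrollment, last visit, contact date or death.

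No minimum follow-up is set, and neither document gives an expected utilization rate.

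**The concern.** The two formulas estimate different quantities under one label. The pooled rate weights each patient by time observed. The mean of ratios gives every patient equal weight, so a patient seen for days counts as much as one seen for years. The SAP figure multiplied by the cohort's person-years would in general not return the number of admissions observed.

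The setting makes this matter. Protocol 7.3 says that "as much as 70% of patients 65 years or older will die of their disease within 1 year of diagnosis" and describes induction treatment at the start. If use clusters around diagnosis and follow-up stops at death, very short denominators meet early events.

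The interval does not match the estimator either. Poisson and negative binomial models describe integer counts with person-time as an offset. They fit the protocol's rate, not non-integer ratios, and a QQ plot does not change that.

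Restoring the protocol formula is not enough by itself. Protocol 9.7 also runs follow-up to enrollment, and SAP 8.7.1 expects deceased patients to be enrolled under a consent waiver. For them, enrollment falls after death, and the years between would count as time at risk.

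**Working it through.** The plan states no PPPY value to reproduce, so the check compares the two definitions under stated assumptions.

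**1. Formulas.** Let X be a patient's count and T that patient's follow-up in years.

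- Protocol: ΣX / ΣT.
- SAP: mean of X/T.
- If use runs at a constant rate r, both have expectation r.
- If there is one admission at diagnosis plus rate r, the protocol form tends to r + 1/E[T] and the SAP form to r + E[1/T]. E[1/T] is never smaller than 1/E[T], and it depends heavily on the shortest follow-up allowed.

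**2. Two patients (illustration only).** One is admitted once and dies on day 10. The other has 8 admissions in 5 years.

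- Follow-up to death: the ratios are 365/10 = 36.5 and 8/5 = 1.6. SAP mean = (36.5 + 1.6)/2 = 19.05. Pooled rate = 9/(5 + 10/365) = 1.79.
- Follow-up to enrollment, taken as 5 years for both: the ratios are 0.2 and 1.6, with mean 0.90. Pooled rate = 9/10 = 0.90.

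So the follow-up rule decides whether the two formulas disagree.

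**3. Simulation inputs.**

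- From the documents: about 700 patients (SAP 8.5), diagnosis 2015 to 2019, data collection July 2021 to August 2022 (Protocol Section 6). Enrollment then falls about 1.5 to 7.7 years after diagnosis.
- Assumed: diagnosis and enrollment dates spread evenly, exponential survival, one-year mortality 30%, 50% or 70%, and the use patterns below. Some runs of the six-month pattern included 20% long-term survivors.
- Each result is the median, over 400 simulated cohorts, of SAP mean divided by pooled rate.

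**4. Results with follow-up ending at death.**

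| Assumed use | SAP mean / pooled rate |
|---|---|
| Constant 2 per year | 0.99 to 1.00 |
| One admission at diagnosis + 2 per year, 50% mortality, minimum follow-up 1 / 7 / 30 days | 2.37 / 1.93 / 1.56 |
| Same, 70% mortality | 2.87 / 2.20 / 1.66 |
| One admission at diagnosis + 1, 2 or 4 per year, whole grid | 1.22 (30%, 4 per year, 30 days) to 3.74 (70%, 1 per year, 1 day) |
| Four admissions over the first 6 months, then 0.5 or 1 per year | 1.44 to 2.30 |

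In the 2.37 case, patients with under one month of follow-up supply about 46% of the summed ratios. In the six-month pattern they supply only 6% to 17%.

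**5. Results with follow-up to enrollment.** The ratio is 1.07 to 1.13. For a true constant rate of 2.0 per year and 50% mortality, the SAP form gives 0.65 and the protocol form 0.59.

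Hand check of the dilution:

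- Mean time from diagnosis to enrollment is about 4.58 years (mid-2017 to the end of January 2022).
- With hazard ln 2 = 0.693, mean time alive within 4.58 years is (1 − e^(−0.693 × 4.58))/0.693 = (1 − 0.042)/0.693 = 1.38 years.
- Diluted rate = 2 × 1.38/4.58 = 0.60.

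**The case against.** The strongest reply is that SAP 8.7 divides by follow-up and, in the same section, defines follow-up as diagnosis to enrollment. Read literally, a patient who dies on day 10 has a denominator of years and no extreme ratio arises. This is right, and it removes most of the gap between the two formulas. It does not rescue the rate, because time after death then enters the denominator of both, and other sections stop the clock at death.

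Other replies carry some weight:

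- Protocol 9.7 lets the SAP modify its plans and asks for an amendment only for major changes to primary endpoints. The change is therefore no breach, only unexplained.
- A mean of individual rates is a legitimate quantity, not an arithmetic error. It is still a different one from the protocol's.
- SAP 8.7 says "Continuous variables will be described as mean and standard deviation (SD), and/or as median, minimum, maximum, interquartile range", so a median may also appear, and item 13 of SAP 8.7.2 already lists the number of hospitalizations. The mean nonetheless remains the named PPPY statistic. Item 13 does not mention PPPY, and the table shells are in an attached file that could not be read.
- A Gamma distribution can describe positive continuous ratios. The mismatch concerns the Poisson and negative binomial options.
- The 70% figure is an upper value for AML patients aged 65 or older. The cohort starts at age 18, includes R/R B-cell ALL and requires at least one treatment line. Protocol 7.3 describes induction but does not say that it is inpatient. Front-loaded use is plausible but not quantified.

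**Conclusion.** The conflict stands on the text alone: two definitions of PPPY, no stated reason for the change, interval methods that do not fit the new one, and several end points for follow-up. The direction and size of the error depend on which follow-up rule is programmed. If it ends at death, the SAP mean is inflated by an illustrative 1.2 to 3.7 times when use is concentrated near diagnosis. If it runs to enrollment, the definitions differ by about 7% to 13% and both understate use.

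Three stronger readings are tempting and not supported:

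- That the SAP mean is about double the protocol's. A factor of two lies inside the simulated range, but it rests on an assumed use pattern, mortality and minimum follow-up that the documents do not give.
- That early deaths alone inflate the mean. At a constant rate the two definitions agree in expectation, and use must also be front-loaded or higher in short-lived patients.
- That comparisons of resource use between countries would be distorted. SAP 8.7.6 stratifies only the primary objectives and EFS, OS and RFS by country.

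Severity is moderate. Resource use is a secondary, descriptive objective with no hypothesis test.

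**What to change.** In SAP 8.7:

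1. Define PPPY as total events divided by total person-years at risk in the cohort, including patients without the event.
2. End person-time at death, last contact or enrollment, whichever is earliest. This agrees with the abstract in Protocol Section 4. Align SAP 8.2.3, the follow-up definition in SAP 8.7, and item 13 of SAP 8.7.2 with it, and note the departure from the follow-up wording in Protocol 9.7.
3. For counts, take the 95% interval from a Poisson or negative binomial model with log person-years as offset.
4. If per-patient ratios are wanted, report them as median and IQR with a stated minimum follow-up, not as mean and SD.

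The cost is a short SAP edit and reprogramming of the affected tables. No new data are needed, provided that the dates of death and last contact, which the survival analyses already require, are captured.

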8.7.1. Analysis Sets

All final analyses identified in this SAP will be performed by IQVIA following Pfizer Authorization of this Statistical Analysis Plan and Database Lock process.

The all subjects enrolled (ENR) set will contain all patients screened for the study, including those who provided the informed consent and the ones enrolled with an informed consent waiver (deceased patients).

The full analysis set (FAS) will contain all eligible patients.

The safety analysis set (SAF) will contain all eligible patients who receive at least one documented dose of any Pfizer product.

If there is any doubt whether a subject was treated or not with a Pfizer product, they will be assumed treated for the purposes of analysis.

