9.10. Other Aspects

All efforts are made in this protocol to reduce inclusion bias. Potential sources of bias in this study, and the approach(es) for addressing and minimizing these biases are discussed below.

Selection bias: may arise if the study sample differs substantively from the underlying target population of patients with B-cell ALL R/R or AML. To minimize selection bias, the study protocol has selected eligibility criteria that are as liberal as possible: age ≥ 18 , newly diagnosed B-cell ALL R/R or AML, and willing to consent, in case ICF waiver is not approved by the ethics committee. Patients will also be recruited from a heterogeneous reservoir of study sites. Finally, where applicable, minimal de-identified information, including the reason for nonparticipation, will be collected for patients who are not enrolled in the study to assess whether there may be any systematic differences between participants and non-participants.

Measurement bias: inaccurate assessment of study variables can occur in observational research. The present study will seek to limit measurement bias by instructing investigators to conduct their patient care in the customary fashion and that observations will be made in a nonintrusive manner that will focus on medical records and not infringe on Latin American healthcare provider's and patient interactions.

Bias due to Missing Data or Study Variables: reference is made to [Section 9.9](#) regarding strategies for handling missing data. Briefly, the impact of missing data on the analysis will be evaluated, and appropriate measures will be taken to address the missing information if any bias is likely.

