10.2. Patient Consent

As this study does not involve data subject to privacy laws according to applicable legal requirements, obtaining informed consent from patients by Pfizer is not required.

This research presents no more than minimal risk of harm to patients and involves no physical procedures with patients, therefore, a waiver of informed consent will be requested as only retrospective collection of anonymized, non-personally identifiable data will be performed. Alternatively, patients will be informed accordingly, and will be asked to give their consent on data handling procedures in accordance with national regulations in place in each of the countries included in the study.

All data will be extracted from patient's medical chart and entered into an electronic CRF specifically designed to capture relevant information in accordance with the study outcomes. Prior to the enrollment of any patient, the study must be evaluated by the local independent ethics committees (IEC) and/or institutional review board (IRB) and a formal approval must be provided.

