8.7.4. Adjustment for Confounding

If possible, the following adjustment for confounding will be performed according to the data availability:

- age
- country
- cytogenetic risk
- ECOG performance status

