8.9. Quality Control

IQVIA Quality Management System (QMS)

At the study level, all aspects of the study from protocol development to the reporting of the results are conducted within the work-frame of IQVIA Quality Management System (QMS) and in accordance with the global procedure RWI_OP_BIOS0006RW: Biostatistics for Non-Interventional Studies and Low Intervention Clinical Trials, and RWI_WI_BIOS0021: Biostatistics Quality Control for Analysis Datasets and Statistical Output, which include quality control on study methodology, statistical analysis plan, programming, data management and analysis, study results, conclusions and study report.

9. Protection of Human Subjects Related to the Analysis

This research presents no more than minimal risk of harm to patients and involves no physical procedures with patients, therefore, a waiver of informed consent will be requested as only retrospective collection of anonymized, non-personally identifiable data will be performed. Alternatively, patients will be informed accordingly, and will be asked to give their consent on data handling procedures in accordance with national regulations in place in each of the countries included in the study.

All data will be extracted from patient's medical chart and entered into an electronic CRF specifically designed to capture relevant information in accordance with the study outcomes. Prior to the enrolment of any patient, the study must be evaluated by the local independent ethics committees (IEC) and/or institutional review board (IRB) and a formal approval must be provided.

10. Management and Reporting of Adverse Events/ Adverse Reactions

Pursuant to the European Medicines Agency (EMA) requirements for reporting of adverse events for secondary data (GVP module VI, VI.C.1.2.1.2), adverse event reporting will not be conducted as part of this study given the study objectives will be met through the use of secondary data.

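### SAP 8.7.1 ties the consent waiver to deceased patients; where living patients must consent, inclusion depends on vital status, and no sensitivity analysis of survival is planned for it

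*SAP*

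**What the plan says.** SAP 8.7.1 says the enrolled set holds everyone screened, "including those who provided the informed consent and the ones enrolled with an informed consent waiver (deceased patients". It adds that "The full analysis set (FAS) will contain all eligible patients", with no split by consent route or vital status.

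Other sections describe consent differently. Protocol 10.2 says "a waiver of informed consent will be requested as only retrospective collection of anonymized, non-personally identifiable data will be performed", with no reference to vital status. SAP section 9 repeats that request and gives the fallback: "Alternatively, patients will be informed accordingly, and will be asked to give their consent on data handling procedures". In its discussion of selection bias, Protocol 9.10 lists among the entry conditions "willing to consent, in case ICF waiver is not approved by the ethics committee". Consent is not among the numbered inclusion criteria in Protocol 9.2.1 or SAP 8.2.5.1.

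Protocol 9.10 also plans, where this applies, that "minimal de-identified information, including the reason for nonparticipation, will be collected for patients who are not enrolled in the study", the purpose being "to assess whether there may be any systematic differences between participants and non-participants". The SAP does not mention this comparison. SAP 8.7.4 says "If possible, the following adjustment for confounding will be performed according to the data availability" and lists age, country, cytogenetic risk and ECOG. The subgroup, missing-data and limitations sections (SAP 8.7.6, 8.7.7 and 8.8) do not refer to consent route.

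**The concern.** Vital status is the OS outcome, and death is an event in EFS and RFS. If deceased patients enter without consent while living patients enter only when reached and willing, sampling depends on the outcome. Kaplan-Meier deals with censoring among the patients who were included; it cannot recover survivors who never entered.

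Diagnoses run from January 2015 to December 2019 and data collection was planned from July 2021 to August 2022, so living patients would have to be traced at least about a year and a half after diagnosis, and often much longer. Median OS and 1-, 3- and 5-year OS are stated secondary objectives. The later percentages rest most heavily on survivors. SAP 8.7.6 also stratifies survival by country, so if consent routes differ between countries, the strata would be distorted unequally.

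**Working it through.** **The plan's own figure.** The country figures in SAP 8.5 add up to the stated total: 200 + 300 + 100 + 100 = 700. This is a feasibility count. The documents contain no precision calculation, consent rate or expected share alive, so every inclusion fraction and survival curve below is an assumption.

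**Formula.** Let A be the share of eligible patients alive at enrolment, c the fraction of the living who are included, d the fraction of the deceased who are included, and S(t) the true survival. Before anyone is censored, the sample shows

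S'(t) = [cA + d(S(t) − A)] / [cA + d(1 − A)].

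This applies at 1 year, because the shortest gap from diagnosis to the planned start of collection is about 1.5 years.

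**One-year OS, S(1) = 0.50 and A = 0.222:**

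- c = 0.7, d = 1: (0.1554 + 0.2780) / (0.1554 + 0.7780) = 0.4334 / 0.9334 = 46.4%.
- c = 0.9, d = 0.7: (0.1998 + 0.1946) / (0.1998 + 0.5446) = 0.3944 / 0.7444 = 53.0%.

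**Later time points.** These come from a simulation of 400,000 patients, with diagnosis uniform over 2015–2019 and enrolment uniform from July 2021 to August 2022. The assumed survival has 20% long-term survivors and exponential deaths among the rest, giving S(1) = 50%; 22% are alive at enrolment.

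| Living included | Deceased included | 1-year OS | 3-year OS | 5-year OS | Median (months) |
|---|---|---|---|---|---|
| 100% | 100% | 50.0% | 24.2% | 20.6% | 12.0 |
| 90% | 100% | 48.8% | 22.5% | 18.8% | 11.5 |
| 70% | 100% | 46.4% | 18.9% | 15.1% | 10.7 |
| 50% | 100% | 43.7% | 14.9% | 11.0% | 9.9 |
| 80% | 80% | 50.0% | 24.2% | 20.5% | 12.0 |
| 90% | 70% | 53.0% | 28.7% | 25.2% | 13.4 |

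In the 70%/100% row the relative loss is 3.6/50.0 = 7% at 1 year, 5.3/24.2 = 22% at 3 years and 5.5/20.6 = 27% at 5 years. Weighting each patient by 1/c or 1/d according to vital status returns the true percentages in every row to within 0.1 point.

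**Poorer survival.** Protocol 7.3 puts 1-year mortality as high as 70% in AML patients aged 65 or older, so take S(1) = 30%. With 10% long-term survivors, true 1/3/5-year OS of 30.0/11.0/10.1% reads 27.7/8.1/7.1% at c = 0.7, d = 1. With no long-term survivors only 1.5% are alive at enrolment, and even c = 0.5 moves 1-year OS only from 30.0% to 29.5%.

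**Weights that depend on misrecorded vital status.** Take 100 eligible patients, of whom 25 are truly alive. Let 80% of those consent (20 enrolled) and let 10% of the 75 deaths be undocumented (7.5, none enrolled), leaving 67.5 deceased enrolled.

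- Unweighted share alive: 20 / 87.5 = 22.9%.
- Undocumented deaths logged as living: the living weight is 32.5/20, and the weighted share is 32.5/100 = 32.5%. This is further from the true 25% than no weighting.
- Those 7.5 counted as deceased: weights 25/20 and 75/67.5, giving 25/100 = 25.0%.

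So patients of unknown status have to be counted both ways, not placed with the living by default.

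**The case against.** A reader might infer from SAP 8.7.1 that every living patient must consent and that survival is therefore biased downward. The documents support neither step.

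- **Consent is conditional.** The deceased-only gloss is a single parenthesis in the definition of the enrolled set, introduced by a word that need not be exhaustive. SAP section 9 and Protocol 10.2 still request a general waiver, and Protocol 9.10 requires consent only where that is refused. At a site with a full waiver this selection would not arise. SAP version 2.0 revised section 8.7 after a test on 20% of the entered data and the parenthesis stands, but the log does not say which lines changed.
- **Direction is open.** Patients with no chart or with unreliable data are excluded, and this may fall more heavily on the deceased. SAP 8.8 concedes that some deaths are not documented, and SAP 8.7 censors OS at the latest of enrolment, last visit and last contact, which credits survival time to such patients. Both push upward.
- **Size may be small.** With 90% of the living and all of the deceased included, each OS percentage in the table moves by less than 2 points.
- **A simple weighting remedy can do harm**, as the last calculation shows.
- **The non-participant log is not assured.** Protocol 9.10 plans it only where applicable, and the current SAP postdates the planned end of data collection (August 2022), so new fields could mean going back to sites and ethics committees.

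All of this stands. It limits the claim to a conditional one and rules out a one-sided correction. It does not explain why the SAP contradicts itself on the waiver, drops the planned comparison and leaves the issue out of its limitations. Uncertainty about size and sign is itself a reason to report inclusion by vital status.

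**Conclusion.** The point holds conditionally. SAP 8.7.1 is inconsistent with SAP section 9 and Protocol 9.10 and 10.2 on who enters under a waiver. Wherever living patients had to consent and some did not enter, the unweighted estimates depend on inclusion fractions that are neither reported nor examined.

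The bias is downward if the living are included less often than the deceased, absent if the fractions are equal, and upward if deceased patients' charts are harder to include. Under the main assumed curve, 5-year OS of about 21% could read anywhere from 11% (half of the living, all of the deceased) to 25% (90% and 70%). Relative effects are largest at 3 and 5 years, and negligible if almost nobody is alive at enrolment. EFS and RFS share the mechanism, but no figures were computed for them.

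These are secondary, descriptive objectives and the main estimate need not change. This is a cheap improvement.

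**What to change.** 1. Reconcile SAP 8.7.1 with SAP section 9 and Protocol 9.10 and 10.2, and state by country or site which consent route applied.
2. From the screened set and, where permitted, the Protocol 9.10 log, report by country and cohort the numbers eligible, consented, refused, unreachable and waiver-enrolled, each by vital status (alive, deceased, unknown).
3. Keep the unweighted Kaplan-Meier as the main estimate. For consent-requiring sites, add a sensitivity analysis of OS, EFS and RFS weighted by the inverse of the inclusion fraction for each vital status, with bootstrap intervals. Count patients of unknown status once as alive and once as deceased. Where no log exists, show the estimate over an assumed range of inclusion fractions, for example 50–100% for the living and for the deceased separately.
4. Add this selection to the limitations in SAP 8.8.

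Cost: a little more analysis and a wider reported range. The weighting assumes that, within strata, included patients resemble those not included, in particular that consenting survivors resemble non-consenting ones. The assumed-range version needs no new data; adding fields to the log could require further site or ethics contact.
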